On December 16, 2021 the CDC published updated recommendations regarding use of the Ad26.COV2.S (Johnson & Johnson) vaccine (<https://www.cdc.gov/media/releases/2021/s1216-covid-19-vaccines.html>) due to the rare but persistent adverse event thrombosis with thrombocytopenia syndrome (TTS) seen with the Ad26.COV2.S vaccine alone. They expressed a clinical preference for individuals to receive an mRNA COVID-19 vaccine over an Ad26.COV2.S vaccine, however, reaffirmed that receiving any vaccine is better than being unvaccinated. This recommendation, however, did not specify stipulations for our currently immunosuppressed patients with cancer population who have already received three prior mRNA COVID-19 vaccines with minimal or no response. Given our patient population remains at high-risk for severe COVID-19 despite three prior mRNA COVID-19 vaccines, we feel the administration and efficacy evaluation of Ad26.COV2.S (Johnson & Johnson) vaccine as a mix and match strategy for booster vaccination continues to remain warranted as part of our study. In fact, a recent study from South Africa does suggest excellent efficacy of a booster Ad26.COV2.S vaccine corroborating this approach¹⁵.

Some patients, however, remain hesitant to receive an Ad26.COV2.S given its rare but potentially severe adverse event as outlined above. Thereby, for study candidates who prefer not be randomized in cohort 2, participation in cohort 3 will be offered. Cohort 3 will be a prospective, non-randomized cohort to address the question of whether a switch mRNA vaccine approach might be more effective at achieving an increased immune response in poor responders to a prior series of three mRNA vaccinations (mRNA-1273 (Moderna) or BNT162b2 (Pfizer/BioNTech)). Eligible patients will be prospectively followed to receive a BNT162b2 vaccine as a fourth dose evaluating their increase in mean SARS-CoV-2 Spike IgG titers above a pre-established threshold by 4 weeks following vaccination as the primary endpoint with further secondary endpoints regarding safety, neutralization antibody and T cell assays and durability of response with assessments at 3, 6, 12 and 24 months. As it is anticipated that about 60-70% of study candidates will have previously received BNT162b2 and 30-40% mRNA-1273, this cohort will allow an assessment of a switch approach in a non-randomized single arm fashion.

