Our proposed study is a prospective single arm study, which will aim in an exploratory/pilot fashion to assess the following variables in a population of patients with cancer with prior vaccination against COVID-19.

- To study the difference in mean titers for SARS-CoV-2 spike IgG in patients with cancer after administering an additional (fourth) booster dose of the BNT162b2 vaccine in patients that had a poor serological response after standard homologous (BNT162b2 → BNT162b2) vs. heterologous (mRNA-1273 → BNT162b2) vaccine series (including a third dose).
- To study safety and side effects from an additional booster dose of the BNT162b2 COVID vaccine

Inclusion criteria:

Our target population consists of patients with a known or previous diagnosis of cancer who had received three prior doses of one of the mRNA based COVID-19 vaccines including a booster dose. Our study will employ the following inclusion criteria:

- Above the age of 18
- Have a diagnosis of prior or active malignancy- either hematological or solid tumor
- Have a negative or low-level SARS-CoV-2 spike IgG after at least 14 days of booster vaccination series irrespective of active/inactive cancer status, on observation, or active therapy.
- Have received an FDA authorized booster dose of mRNA (BNT162b2 or mRNA 1273) vaccine at least 28 days before study enrollment

- Decline to participate in cohort 2 requiring randomization of BNT162b2 and Ad26.CoV2.S vaccines

Exclusion Criteria

- Patients who have had a serious adverse reaction to any prior COVID-19 vaccines resulting in emergency room visit or hospitalization, had events related to myocarditis, thrombosis and thrombocytopenia syndrome or anaphylaxis to any prior dose of the COVID-19 vaccines.
- Patients who have had a documented COVID-19 infection in the 90 days prior to study enrollment

Outcomes

Primary outcome: To compare the increase in mean titers for SARS-CoV-2 spike antibody after 4 weeks following a homologous (BNT162b2 → BNT162b2) vs. heterologous (mRNA-1273 → BNT162b2) additional booster dose of COVID vaccine in patients that had a poor serological response after standard vaccine series (including a third dose).

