Cohort 3. Our null hypothesis is that the additional homologous booster vaccine dosing with the BNT162b2 after prior BNT162b2 vaccination will increase mean titers in the spike IgG assay by at least 300%. Alternate hypothesis is that heterologous vaccination with the BNT162b2 after prior mRNA-1273 vaccination will increase mean titers by an additional 300%- that is to 600%. To achieve 80% power at a significance level alpha = 0.05, a one sided two sample t-test would require 22 samples per group to detect differences in mean titers of 750 AU/mL and 1500 AU/mL at an estimated standard deviation of 1000 AU/mL. Given we estimate 30-40% patients with have had prior mRNA-1273 vaccination and accounting for 5% dropout rate, we will thus use a planned sample size of 80.

Statistical analysis

To assess our goals as outlined above, statistical analysis will be done in the R software environment. The primary aim of cohorts 1 and 2 examining the seroconversion rates after 4 weeks will be checked with a one sample z test of proportions. The primary aim of cohort 3 examining the increase in mean Spike IgG titers will be checked with a one sided two sample t-test. Secondary aims involving the significance of associations between certain malignancies and the rates of seroconversion in our prospective single arm study will be measured by Fisher's exact and Cochran- Mantel-Haenszel tests depending on if analysis is conducted by a stratified variable (Cochran- Mantel-Haenszel) or not (Fisher's exact). The more complicated relationship between patients' seroconversion rates, their recent receipt of medical treatment, and additional factors such as history of malignancy will be examined through a multivariate logistic

regression model. After addressing the appropriateness of interaction terms, a Wald test will be used to consider the statistical significance of all included variables at the $p < 0.05$ level.

Duration

Our study will follow patients from Aug 1, 2021 through November 2023, which will allow for sufficient time to assess follow-up serologies after COVID-19 vaccination infection in patients with cancer (24 months follow up).

Matching

Cohort 1

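### Cohort 3's primary endpoint has no single scale, and its unadjusted t-test on non-randomised groups lets unequal starting titres, or a few high responders, drive the result

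*Combined protocol and SAP*

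**What the plan says.** The Cohort 3 endpoint appears in four places.

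- **Cohort 3, introductory text:** "increase in mean SARS-CoV-2 Spike IgG titers above a pre-established threshold by 4 weeks following vaccination as the primary endpoint". No threshold value is given for this cohort. The figure of >1000 AU/ml in the sample-size section belongs to Cohort 2.
- **Cohort 3, Outcomes:** "To compare the increase in mean titers for SARS-CoV-2 spike antibody after 4 weeks", homologous versus heterologous. No scale is named.
- **Sample size, Cohort 3, hypotheses:** the homologous dose "will increase mean titers in the spike IgG assay by at least 300" percent. The heterologous dose "will increase mean titers by an additional 300%- that is to 600" percent.
- **Sample size, Cohort 3, calculation:** 22 per group "to detect differences in mean titers of 750 AU/mL and 1500 AU/mL at an estimated standard deviation of 1000 AU/mL", one-sided, with 80% power and alpha 0.05. The planned total is 80, allowing for a 30-40% mRNA-1273 share and 5% dropout.

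The Statistical analysis section repeats the one-sided two-sample t-test. No section mentions a log transformation, a geometric mean, a per-patient fold rise or adjustment for starting titre in the primary comparison.

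Cohort 3 is non-randomised, and its two groups are defined by prior vaccine. Entry requires negative or low-level spike IgG, with no upper limit given for low-level. Under Planned intervention, Cohort 2 is stratified on negative versus low-positive antibody, described there as a key confounder. Cohort 3 has no counterpart.

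**The concern.** A relative rise and an AU/mL difference are different estimands, and they can rank the same two groups differently when starting titres differ. An analyst could follow the hypothesis, the sample-size calculation or the introductory text and report different primary results, each defensible from the plan.

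Starting titre is where this matters most. Patients with three prior mRNA-1273 doses may enter with different titres from those with three BNT162b2 doses. If a booster multiplies titre, the group that starts higher shows the larger AU/mL rise even when the vaccine sequence makes no difference. The planned test cannot separate that from a benefit of switching. In addition, an SD (1000) larger than the lower mean (750) suggests a long right tail, in which a few patients can carry a group mean.

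**Working it through.** **1. The plan's own figure.** Inputs from Sample size, Cohort 3: difference 1500 - 750 = 750, SD 1000, one-sided alpha 0.05, power 80%.

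n per group = 2 × (1.645 + 0.842)² × (1000/750)² = 12.365 × 1.778 = 21.98, so 22. This reproduces. The exact t calculation gives 78.9% power at 22 and needs 23 for 80%, a trivial difference.

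Total: 22 / 0.30 / 0.95 = 77.2, which 80 covers. Completers: 80 × 0.95 = 76. At a 30% share that is about 23 prior mRNA-1273 and 53 prior BNT162b2.

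**2. When percent and AU/mL agree.** Let B be a common mean starting titre.

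- If 750 and 1500 are rises: 3B = 750 and 6B = 1500 both give B = 250.
- If they are 4-week levels: (1 + 3)B = 750 gives 187.5, and (1 + 6)B = 1500 gives about 214. No common start fits.

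The plan states no baseline. Holding SD at 1000, the gap between a 300% and a 600% rise is 3B AU/mL, and the required size follows:

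| Mean start (AU/mL) | Gap (AU/mL) | n per group |
|---|---|---|
| 100 | 300 | 138 |
| 187.5 | 562.5 | 40 |
| 250 | 750 | 22 |
| 500 | 1500 | 6 |

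**3. Effect of unequal starting titres.** Simulation, 20,000 runs, 53 versus 23 completers, the same median 4-fold rise in both groups. Assumed (not in the documents): log-normal titres, log SD 0.5 at baseline and about 1.0 for the rise. The table gives the share of runs with one-sided p < 0.05 in favour of the switch.

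| Mean baseline, BNT162b2 / mRNA-1273 | t-test on AU/mL rise |
|---|---|
| 250 / 125 | under 0.1% |
| 250 / 250 | 6% |
| 250 / 375 | 29% |
| 250 / 500 | 56% |

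A linear model of log 4-week titre on group, adjusted for log baseline titre, stays near 5% in all four rows.

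**4. Effect of a few high responders.** A normal distribution with mean 750 and SD 1000 has Φ(-0.75) = 22.7% of its mass below zero. That is impossible for a titre level. For a rise it makes skew likely without proving it. Assume log-normal titres with the plan's CV: log SD = √ln(1 + (1000/750)²) = √ln 2.778 = 1.01. With a true 2-fold ratio and 53 versus 23 completers, the top 2 of 23 heterologous patients then carry about 31% of their group's total. Dropping them overturns about 42% of the significant raw-scale results.

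**5. Power on a log scale.** Target ratio 1500/750 = 2, ln 2 = 0.693, and n = 12.365 × (log SD / 0.693)². This is an unadjusted two-group comparison. The log SD is an assumption.

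| Log SD | n per group | Power at 53 vs 23 |
|---|---|---|
| 1.01 | 27 | about 86% |
| 1.25 | 41 | about 71% |
| 1.5 | 58 | about 57% |

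**The case against.** **The percent and AU/mL statements need not conflict.** The percentages refer to group means, and they coincide with the AU/mL figures if those are rises from 250. A reader might infer a contradiction or a sample-size error. The documents support neither: the arithmetic reproduces, and the fault is an unstated baseline and an unstated quantity.

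**The log scale is not shown to be more powerful.** A reader might infer a general gain from log-normal simulations in which everyone responds. The Cohort 2 introduction says many patients do not respond, or respond with very low titres. Placing an assumed share of both groups at a floor of 10 AU/mL (53 versus 23, means about 750 and 1500, equal CV) gives raw versus log power of 70% versus 49% at 10% non-responders, and 64% versus 32% at 20%. The objection stands, and no power gain is claimed here.

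**An unadjusted fold rise would not cure the problem.** With identical 4-week titres but 40% versus 60% of patients starting negative (set to 10 AU/mL, the rest around 300), the unadjusted log fold-rise test is significant in 39% of runs and the AU/mL-rise test in 10%. This stands too, and it is why the fix adjusts for baseline. The adjusted log model stays near 5% in this setting as well.

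**Raw arithmetic means are an inference.** The documents never use those words. The inference is strong, given mean titres, an SD in AU/mL and a t-test.

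**The cohort is described as exploratory or pilot.** That lowers the stakes, but the plan still sets a powered hypothesis test for it.

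**Conclusion.** The concern holds in a limited form. The plan does not fix the scale of Cohort 3's primary endpoint, does not say whether 750 and 1500 are rises or levels, and attaches a threshold without a value. The comparison is non-randomised and unadjusted for a variable that the plan itself treats as a key confounder in Cohort 2.

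Under the stated assumptions, a baseline mean 1.5 times higher in the mRNA-1273 group raises the false-positive rate of the AU/mL-rise test from about 6% to 29%, and a mean twice as high raises it to 56%. An imbalance the other way would hide a benefit. The documents give no baseline titres or titre distribution, so these rates show what can happen, not what will. It would go too far to say that high responders or baseline imbalance do decide the answer. This should be corrected, but it does not invalidate the cohort or its stated sample size.

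**What to change.** Use the same wording in the Cohort 3 introduction, its Outcomes section, and the Sample size and Statistical analysis sections:

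- **Estimand:** the ratio of geometric mean 4-week spike IgG titres, prior mRNA-1273 versus prior BNT162b2.
- **Analysis:** a linear model of log 4-week titre on group, adjusted for log initial-visit titre and for negative versus low-positive status, with low-positive defined for this cohort.
- **Results below the assay limit:** one fixed value at both visits, with a sensitivity analysis to that value.
- **Hypothesis and size:** state the hypothesis as a ratio, say whether 750 and 1500 are rises or levels, and restate power at the planned 80 with a stated and justified log-scale SD.
- **Threshold:** remove it from the introduction, or give its value and make the share of patients above it a named secondary outcome.
- **AU/mL means:** keep them as descriptive.

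The cost is wording and a revised power statement. Spike IgG at the initial visit and at day 28 is already in the Cohort 3 study calendar. The downsides are that the result reads as a ratio instead of an AU/mL difference, that it depends somewhat on the floor value, and that the restated power may be below 80%.

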Have received an FDA authorized booster dose of mRNA (BNT162b2 or mRNA 1273) vaccine at least 28 days before study enrollment

Exclusion Criteria

Patients who have had a serious adverse reaction to any prior COVID-19 vaccines resulting in emergency room visit or hospitalization, had events related to myocarditis, thrombosis and thrombocytopenia syndrome or anaphylaxis to any prior dose of the COVID-19 vaccines.

Patients who have had a documented COVID-19 infection in the 90 days prior to study enrollment

Outcomes

Primary outcome: Rates of seroconversion for SARS-CoV-2 spike antibody after 4 weeks following an additional booster dose of BNT162b2/AdCov2.S COVID vaccine in patients that had a poor serological response after standard vaccine series (allowing additional booster dose)

Secondary outcomes: Safety of booster dose of BNT162b2 and AdCov2.S vaccines, correlation between malignancy type and prior treatment type and seroconversion, correlation between timing of most recent cancer-directed treatment and seroconversion, correlation between the total number of cancer-directed treatments received and seroconversion, differences between booster efficacy dependent on prior vaccine type (BNT162b2 versus mRNA-1273), T cell responses at baseline and 4 weeks following vaccination, Antigen neutralization assay results at baseline and 4 weeks following vaccination, duration of sustained immunogenicity following vaccination in seropositive patients, correlations with baseline immune status correlates such as lymphocyte subsets/immune globulin levels

Safety monitoring.

Patients who have met all eligibility criteria will then be randomized 1:1 to receive either the BNT162b2 or AdCov2.S and then will be scheduled to receive their study dose at the Montefiore Vaccine Center. Each patient will be observed for a minimum of 15 minutes after their vaccination to monitor for any adverse

effects in the Montefiore Vaccine Center as per the Vaccine Center protocol.

Cohort 3

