Cohort 1. For a 1 sample test of proportions our hypothesis is that booster vaccine dosing will induce detectable immunity by the spike IgG assay in at least 20% of individuals. Null hypothesis is a positivity rate of 10% to account for some test variability and therefore the alternative hypothesis is $p > 30\%$. Our planned sample size of up to 250 will have ample power ($>95\%$) to detect such a difference in our primary endpoint and will still retain 80% power and 5% significance in the secondary preplanned subset analyses as long as cohort sizes per subset are >26 . We anticipate the large majority of patients will be hematologic malignancy patients and such preplanned subset analyses will include two cohorts, the highly immune suppressed (prior anti- CD20, CAR-T, or SCT therapy), and all others (solid tumor/hematologic malignancy patients) who do not fall into the first cohort. We anticipate cohort sizes of at least 26 per cohort based on the numbers of seronegative patients identified in our prior study.

Cohort 2. Our null hypothesis is that the additional homologous booster vaccine dosing will induce detectable immunity (positive spike IgG test result higher than the predefined threshold for seropositivity—i.e. >1000 AU/ml) by the spike IgG assay in at least 25% of individuals. Alternate hypothesis is that heterologous vaccination with the AdCov2.S vaccine will increase this seroconversion rate by an additional 25%- that is to 50%. With an alpha of 0.05 and 80% power to detect the difference, we would require a sample size of 46 in each group. Accounting for 5% dropout rate, we will thus use a planned sample size of up to 100 subjects. We anticipate the large majority of patients will be hematologic malignancy patients and such preplanned subset analyses will include two cohorts, the highly immune suppressed (prior anti-CD20, CAR-T, or SCT therapy), and all others (solid tumor/hematologic malignancy patients) who do not fall into the first cohort.

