Patients would serve as their own control. Baseline seropositivity rate by definition is 0% for the cohort but anticipating natural and laboratory variation we have based on statistical null hypothesis around a 10% seropositivity rate at 4 weeks and anticipate that booster vaccination will increase this to higher than 30%.

Planned intervention

Cohort 1

The planned intervention is to administer a booster dose of the BNT162b2 (Pfizer/BioNTech) or mRNA-1273 (Moderna) vaccine to patients that meet FDA/CDC criteria of cancer on active therapy or patients that have received a stem cell transplantation or CAR-T cell therapy in the last 2 years or those that have a negative spike IgG after having = completed one of the FDA's Emergency Use Authorized vaccination series for COVID-19 (i.e. 2 doses of the mRNA-based mRNA-1273 (Moderna), BNT162b2 (Pfizer/BioNTech), or a single dose of the adenovirus-based Ad26.COV2.S (Johnson & Johnson) vaccine, following completion of their vaccination series.

Cohort 2

The planned intervention is to administer an additional booster dose of the BNT162b2 (Pfizer/BioNTech) or Ad26.COV2.S (Johnson & Johnson) vaccine to patients that meet eligibility criteria for cohort 2 in a 1:1 randomization fashion with negative spike antibody vs. low positive antibody level serving as a stratification factor to ensure controlling for key confounder.

Cohort 3

The planned intervention is to administer an additional booster dose of the BNT162b2 (Pfizer/BioNTech) vaccine to patients that meet eligibility criteria for cohort 3 in a prospective single arm fashion in patients that had a poor serological response after standard vaccine series (including a third dose).

Participant recruitment

The study will both utilize data from the electronic health record to identify patients meeting the above inclusion criteria and enroll them on to the study and accept patients self-referred or referred by their provider at Montefiore Medical Center or external institutions. A consenting visit will be scheduled with each prospective patient. Following a carefully conducted and documented informed consent process subjects who consent for study participation will then be screened. Patients who qualify for booster COVID-19 vaccination as per FDA/CDC guidance and study criteria will then participate in our study.

Data and Safety Monitoring Plan

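### Cohort 2 is a randomised two-arm comparison, but its primary outcome is assigned a one-sample z test that leaves out the concurrent BNT162b2 arm

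*Combined protocol and SAP*

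**What the plan says.** The Statistical analysis section gives cohorts 1 and 2 one shared primary test: "The primary aim of cohorts 1 and 2 examining the seroconversion rates after 4 weeks will be checked with a one sample z test". It gives no reference value for cohort 2 and does not say which arm, or whether the pooled arms, would be tested.

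Everything else about cohort 2 describes a two-arm comparison:

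- **Allocation** (Cohort 2, Safety monitoring): patients are "randomized 1:1 to receive either the BNT162b2 or AdCov2.S".
- **Stratification** (Planned intervention, Cohort 2): "negative spike antibody vs. low positive antibody level serving as a stratification factor to ensure controlling for key confounder".
- **Hypotheses** (Sample size, Cohort 2): under the null, homologous boosting produces a titre above 1000 AU/ml "by the spike IgG assay in at least 25% of individuals". The alternative reads: "Alternate hypothesis is that heterologous vaccination with the AdCov2.S vaccine will increase this seroconversion rate by an additional 25%- that is to 50" (per cent).
- **Size** (same paragraph): alpha 0.05, 80% power, 46 per group, 5% dropout, up to 100 in total. Sidedness is not given.

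No between-arm test of the cohort 2 primary outcome appears anywhere. Fisher's exact and Cochran-Mantel-Haenszel tests are assigned to secondary associations with malignancy in a single-arm setting. The logistic model does not list randomised arm as a term. Cohort 3, which is not randomised, does receive a two-sample test.

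**The concern.** Randomisation gives cohort 2 an unbiased concurrent control. A one-sample test discards it. Applied to the Ad26.COV2.S arm, it asks whether that arm exceeds a fixed number. Applied to the pooled arms, it says nothing about which vaccine does better. Neither answers the cohort's question, which is whether switching vaccine improves on repeating an mRNA dose.

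The stated null has the same defect. A homologous rate of 25% or more is a statement about one arm, and it is compatible with both arms being at 50%. It is not a hypothesis of no difference.

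Two things are at stake. If the true BNT162b2 rate is above 25%, an Ad26.COV2.S arm that is no better can still pass the test. If it is below 25%, a real advantage can be missed. The stratification factor, described in the protocol as a key confounder, also has no role in the primary analysis.

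**Working it through.** **Inputs.** From Sample size, Cohort 2: p1 = 0.25, p2 = 0.50, alpha 0.05, power 0.80, 46 per group, 5% dropout. The reference value p0 = 0.25 for a one-sample test is inferred from the same paragraph, as the only candidate. All other true rates below are assumptions chosen to show a range.

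**Step 1: which test gives 46?** Two-sample, pooled variance under the null, mean rate 0.375:

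n = [z_α·√(2 × 0.375 × 0.625) + 0.842·√(0.25 × 0.75 + 0.50 × 0.50)]² / 0.25²

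- One-sided 0.05 (z_α = 1.645): (1.645 × 0.6847 + 0.842 × 0.6614)² / 0.0625 = (1.126 + 0.557)² / 0.0625 ≈ 45.3, so **46**. This matches the plan.
- Two-sided 0.05 (z_α = 1.960): (1.342 + 0.557)² / 0.0625 ≈ 57.7, so 58.

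One-sample against 0.25:

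n = [z_α·√(0.25 × 0.75) + 0.842·√(0.50 × 0.50)]² / 0.25²

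- One-sided: (0.712 + 0.421)² / 0.0625 ≈ 20.5, so 21.
- Two-sided: (0.849 + 0.421)² / 0.0625 ≈ 25.8, so 26.

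Cohort 2 was therefore sized for a two-sample test. Dropout also fits: 92 / 0.95 = 96.8, so 97, within the limit of 100.

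**Step 2: false claims when the vaccines are equal.** The one-sample statistic on the Ad26.COV2.S arm is z = (p̂ − 0.25) / √(0.25 × 0.75 / n). With n = 46 it exceeds 1.645 from 17 responders upward, and 1.960 from 18 upward. Exact binomial probability of finding the arm above 25%:

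| Common true rate in both arms | n = 46, one-sided 5% | n = 46, two-sided 5% (upper tail) | n = 50, one-sided 5% | n = 50, two-sided 5% (upper tail) |
|---|---|---|---|---|
| 20% | 0.6% | 0.2% | 0.6% | 0.3% |
| 25% | 4.8% | 2.4% | 5.5% | 2.9% |
| 30% | 19.1% | 11.8% | 21.8% | 14.1% |
| 35% | 44.5% | 32.8% | 49.4% | 37.8% |
| 40% | 71.4% | 60.3% | 76.3% | 66.4% |

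A two-sample pooled z test at 46 per arm, enumerated exactly, rejects with probability 4.6% to 5.5% over the same rates.

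**Step 3: missed benefit when the control rate is low.** Take BNT162b2 at 10% and Ad26.COV2.S at 35%, the same 25-point gain, with 50 per arm and two-sided 5%. The one-sample test has 38% power (the 35% row above, 37.8%). The two-sample test has 88%.

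**Step 4: power after correction, at the plan's 25% versus 50%.** Normal approximation:

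| Evaluable per arm | One-sided 5% | Two-sided 5% |
|---|---|---|
| 46 | 80.5% | 70.4% |
| 47 (50 less 5%, rounded down) | 81.3% | 71.3% |

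A two-sided test needs 58 per arm for 80% power. With 5% dropout that is 58 / 0.95 = 61.05, so 62 per arm and 124 in total.

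**The case against.** The strongest reply is that this is a drafting slip. The 46 per group is a two-sample number, the hypotheses contrast homologous with heterologous boosting, and the test sentence reads like cohort 1 wording extended to cohort 2. The plan never says that cohort 2 will be tested against 25%, and it calls the cohort exploratory. If the BNT162b2 rate really is 25%, the one-sample test has close to nominal error (4.8% one-sided at n = 46). At the plan's own alternative of 50% its nominal power is higher than planned, at 97.5% one-sided or 95.5% two-sided.

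A slip is plausible, and the 25% reference is an inference. Neither point supplies the missing test. As written, no between-arm primary analysis is prespecified, so the test, its sidedness and the use of strata could all be settled after the data are seen. The exploratory label does not help when the plan states a hypothesis, an alpha and a power. Near-nominal error at exactly 25% is no safeguard either: the figure has no source, and the stated null itself allows higher rates.

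Three points on the other side do stand. Results at 46 per arm fit the plan better than those at 50, and they are somewhat less extreme. An unstratified two-sample test would also be valid, so stratification is good practice and not a condition of validity. Correcting the test also exposes the unstated sidedness, which has a cost in power or sample size.

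**Conclusion.** The concern holds and must be fixed. The Statistical analysis section contradicts the design, hypotheses and sample size of cohort 2, and it leaves the only randomised comparison in the study without a valid primary test.

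The size of the harm depends on how far the true BNT162b2 rate lies from 25%. With 46 per arm and equally effective vaccines, a common rate of 35% gives a false finding 33% of the time (upper tail, two-sided) or 44% (one-sided). A common rate of 40% gives 60% or 71%. If the common rate is 25%, error is close to nominal. These figures assume that the test is applied to the Ad26.COV2.S arm against 25%. That the named test makes no between-arm comparison does not depend on those assumptions.

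**What to change.** In the Statistical analysis section, keep the one-sample z test for cohort 1 only and add for cohort 2:

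- **Null hypothesis:** equal proportions with spike IgG above 1000 AU/ml at 4 weeks in the two arms. Amend the null in the Sample size section to match.
- **Test:** a comparison of the arms as randomised, by a Cochran-Mantel-Haenszel test stratified by baseline negative versus low-positive antibody. The plan already names this test, though only for secondary associations.
- **Estimate:** the stratified risk difference with its 95% confidence interval.
- **Sidedness:** stated explicitly.

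The wording costs a few sentences and needs no new data. The choice of sidedness has its own cost. A one-sided 5% test keeps 46 per group and the limit of 100. A two-sided 5% test, which is the one that corresponds to a 95% interval, means either accepting and stating about 70% power at 46 per arm, or raising the total to about 124. The choice should be made and recorded before any comparison of outcomes by arm.
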